2 BASELINE DOCUMENTATION OF 'TARGET' AND 'NONTARGET' LESIONS

Target lesions: When more than 1 measurable lesion is present at baseline, all lesions up to a maximum of 5 lesions total (and a maximum of 2 lesions per organ) representative of all involved organs should be identified as target lesions and will be recorded and measured at baseline.

Target lesions should be selected on the basis of their size (lesions with the longest diameter), be representative of all involved organs, and should lend themselves to reproducible, repeated measurements.

Lymph nodes merit special mention since they are normal anatomical structures, which may be visible by imaging even if not involved by tumor. Pathological nodes, which are defined as measurable and may be identified as target lesions, must meet the criterion of a short axis of ≥ 15 mm by CT scan. Only the short axis of these nodes will contribute to the baseline sum. All other pathological nodes (those with short axis ≥ 10 mm but < 15 mm) should be considered nontarget lesions. Nodes that have a short axis < 10 mm are considered nonpathological and should not be recorded or followed.

A sum of the diameters (longest for nonnodal lesions, short axis for nodal lesions) for all target lesions will be calculated and reported as the baseline sum diameters. The baseline sum diameters will be used as reference to further characterize any objective tumor regression in the measurable dimension of the disease.

Nontarget lesions: All other lesions (or sites of disease) including pathological lymph nodes should be identified as nontarget lesions and should also be recorded at baseline. Measurements are not required, and these lesions should be followed as 'present,' 'absent,' or 'unequivocal progression.' In addition, it is possible to record multiple nontarget lesions involving the same organ as a single item on the case record form (eg, 'multiple enlarged pelvic lymph nodes' or 'multiple liver metastases').

3 TUMOR RESPONSE EVALUATION AND RESPONSE CRITERIA

3.1 Evaluation of Target Lesions

Complete Response (CR): Disappearance of all target lesions. Any pathological lymph nodes (whether target or nontarget) must have reduction in short axis to < 10 mm.

Partial Response (PR): \geq 30% decrease in the sum of diameters of target lesions, taking as reference the baseline sum diameters.

Progressive Disease (PD): \geq a 20% increase in the sum of diameters of target lesions, taking as reference the smallest sum on study (this includes the baseline sum if that is the smallest on study). In addition to the relative increase of 20%, the sum must also demonstrate an absolute increase of ≥ 5 mm. Note: The appearance of 1 or more new lesions is also considered progression.

Stable Disease (SD): Neither sufficient shrinkage from the baseline study to qualify for PR nor sufficient increase to qualify for PD, taking as reference the smallest sum diameters while on study.

Special notes on the assessment of target lesions

- Lymph nodes: Lymph nodes identified as target lesions should always have the actual short axis measurement recorded and should be measured in the same anatomical plane as the baseline examination, even if the nodes regress to below 10 mm on study. This means that when lymph nodes are included as target lesions, the 'sum' of lesions may not be zero even if CR criteria are met since a normal lymph node is defined as having a short axis of < 10 mm.
- Target lesions that become 'too small to measure': All lesions (nodal and nonnodal) recorded at baseline should have their actual measurements recorded at each subsequent evaluation, even when very small (eg, 2 mm). If the radiologist is able to provide an actual measure, that should be recorded, even if it is below 5 mm.

However, when such a lesion becomes difficult to assign an exact measure to then:

- (i) if it is the opinion of the radiologist that the lesion has likely disappeared, the measurement should be recorded as 0 mm.
- (ii) if the lesion is believed to be present and is faintly seen but too small to measure, a default value of 5 mm should be assigned (note: in case of a lymph node believed to be present and faintly seen but too small to measure, a default value of 5 mm should be assigned in this circumstance as well). This default value is derived from the 5-mm CT slice thickness (but should not be changed with varying CT slice thickness).

Lesions that split or coalesce on treatment: When nonnodal lesions 'fragment,' the longest diameters of the fragmented portions should be added together to calculate the target lesion sum. Similarly, as lesions coalesce, a plane between them may be maintained that would aid in obtaining maximal diameter measurements of each individual lesion. If the lesions have coalesced such that they are no longer separable, the vector of the longest diameter in this instance should be the maximal longest diameter for the 'coalesced lesion'.

3.2 Evaluation of Nontarget Lesions

While some nontarget lesions may actually be measurable, they need not be measured and instead should be assessed only qualitatively at the timepoints specified in the protocol.

CR: Disappearance of all nontarget lesions and normalization of tumor marker level. All lymph nodes must be nonpathological in size (< 10 mm short axis).

Non-CR/NonPD: Persistence of 1 or more nontarget lesion(s) and/or maintenance of tumor marker level above the normal limits.

PD: Unequivocal progression of existing nontarget lesions. Note: The appearance of 1 or more new lesions is also considered progression.

- The concept of progression of nontarget disease requires additional explanation as follows:
- When the patient also has measurable disease: To achieve 'unequivocal progression' on the basis of the nontarget disease, there must be an overall level of substantial worsening in nontarget disease such that, even in presence of SD or PR in target disease, the overall tumor burden has increased sufficiently to merit discontinuation of therapy. A modest 'increase' in the size of 1 or more nontarget lesions is usually not sufficient to qualify for unequivocal progression status.
- When the patient has only nonmeasurable disease: To achieve 'unequivocal progression' on the basis of the nontarget disease, there must be an overall level of substantial worsening such that the overall tumor burden has increased sufficiently to merit discontinuation of therapy. A modest 'increase' in the size of 1 or more nontarget lesions is usually not sufficient to qualify for unequivocal progression status. Because worsening in non-target disease cannot be easily quantified (by definition: if all lesions are nonmeasurable), a useful test that can be applied when assessing patients for unequivocal progression is to consider if the increase in overall disease burden based on the change in nonmeasurable disease is comparable in magnitude to the increase that would be required to declare PD for measurable disease, ie, an increase in tumor burden representing an additional 73% increase in 'volume' (which is equivalent to a 20% increase diameter in a measurable lesion). Examples include an increase in a pleural effusion from 'trace' to 'large,' an increase in lymphangitic disease from localized to widespread, or may be described in protocols as 'sufficient to require a change in therapy.' If 'unequivocal progression' is seen, the patient should be considered to have had overall PD at that point.

3.3 New Lesions

The appearance of new malignant lesions denotes disease progression. The finding of a new lesion should be unequivocal, ie, not attributable to differences in scanning technique, change in imaging modality, or findings thought to represent something other than tumor (eg, some 'new' bone lesions may be simply healing or flare of pre-existing lesions). This is particularly important when the patient's baseline lesions show PR or CR. For example, necrosis of a liver lesion may be reported on a CT scan report as a 'new' cystic lesion, which it is not.

A lesion identified on a follow-up study in an anatomical location that was not scanned at baseline is considered a new lesion and will indicate disease progression. An example of this is the patient who has visceral disease at baseline and while on study has a CT or MRI brain ordered, which reveals metastases. The patient's brain metastases are considered to be constituted PD even if he/she did not have brain imaging at baseline.

If a new lesion is equivocal, for example, because of its small size, continued therapy and follow-up evaluation will clarify if it represents new disease. If repeat scans confirm that there is a new lesion, then progression should be declared using the date of the initial scan.

3.4 Tumor Markers

Tumor markers alone cannot be used to assess objective tumor responses. If markers are initially above the upper normal limit, however, they must normalize in order for a patient to be considered as having attained a CR.

4 EVALUATION OF BEST OVERALL RESPONSE

4.1 Timepoint Response

A response assessment should occur at each timepoint specified in the protocol.

For patients who have measurable disease at baseline, Table 4.1-1 provides a summary of the overall response status calculation at each timepoint.

Table 4.1-1:Summary of the Overall Response Status Calculation [Timepoint Response: Patients with Target (+/-) Nontarget Disease]				
Target Lesions	Nontarget Lesions	New Lesions	Overall Response	
CR	CR	No	CR	
CR	Non-CR/non-PD	No	PR	
CR	Not evaluated	No	PR	
PR	Non-PD or not all evaluated	No	PR	
SD	Non-PD or not all evaluated	No	SD	
Not all evaluated	Non-PD	No	NE	
PD	Any	Yes or No	PD	
Any	PD	Yes or No	PD	
Any	Any	Yes	PD	

NE = not evaluable.

4.2 Missing Assessments and Inevaluable Designation

When no imaging/measurement is done at all at a particular timepoint, the patient is not evaluable (NE) at that timepoint. If only a subset of lesion measurements is made at an assessment, usually the case is also considered NE at that timepoint, unless a convincing argument can be made that the contribution of the individual missing lesion(s) would not change the assigned timepoint response. This would be most likely to happen in the case of PD.

4.3 Best Overall Response - All Timepoints

Best response determination in trials where confirmation of CR or PR **is** required: CRs or PRs may be claimed only if the criteria for each are met at a subsequent timepoint as specified in the protocol. In this circumstance, the best overall response can be interpreted as in Table 4.3-1. In the case of SD, measurements must have met the SD criteria at least once after study entry at a minimum interval of 7 weeks or approximately 8 weeks.

No.: 03 Date: 03-May-2017
For equivocal findings of progression (eg, very small and uncertain new lesions; cystic changes or necrosis in existing lesions), treatment may continue until the next scheduled assessment. If at the next scheduled assessment, progression is confirmed, the date of progression should be the earlier date when progression was suspected.

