The screening period will last for up to 28 days. Screening period begins after establishing the subject's initial eligibility and the subject's signing of the ICF. Specimens from tumor tissue must be provided (see Section 3.3.1 for details). The screening period either ends with confirmation of full eligibility and treatment assignment of the subject or with the confirmation that the subject is a screen failure. For information on re-screening, see Section 4.4. For details on re-enrollment, see Section 3.3.1.

Treatment Period:

Each treatment cycle consists of an IV infusion of BMS-986183 monotherapy (BMS-986183 dose escalation [Part 1] and BMS-986183 dose expansion [Part 2]) or BMS-986183 and nivolumab (BMS-986183 and nivolumab dose escalation [Part 3] and BMS-986183 and nivolumab dose expansion [Part 4]) once every 21 days. BMS-986183 monotherapy or BMS-986183 and nivolumab combination therapy will be given on Day 1 of each treatment cycle. The study drug is administered for approximately 1 year (17 cycles, with 21 days/cycle) or until complete remission, progression, unacceptable toxicity, withdrawal of consent, or study closure, whichever occurs first. Study assessments are to be collected as outlined in Table 5.1-1 and Table 5.1-2. Specific requirements for subjects treated with BMS-986183, including dose modifications, dose delays, and treatment discontinuation criteria are described in Section 4.5.2, Section 4.5.4, and Section 3.5, respectively. The treatment period ends when the subject is discontinued from study drug (see Section 3.5). Subjects will then enter the safety follow-up period.

Subjects with a response of SD, PR, or complete response (CR) at the end of a given cycle will continue to the next treatment cycle. Subjects with a confirmed CR at the end of the next cycle will discontinue treatment. Subjects will generally be allowed to continue study therapy for approximately 1 year (17 cycles, with 21 days/cycle) or until the subject meets criteria for discontinuation of study therapy as outlined in Section 3.5, whichever comes first.

Individual subjects with SD or PR may have 6 months (9 cycles, with 21 days/cycle) of extended treatment with BMS-986183 after the first treatment period (17 cycles, with 21 days/cycle) on a case-by-case basis after specific consultation and agreement between the investigator and BMS medical monitor.

Follow-up Period:

Safety Follow-up Period

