The end of cycle tumor assessments will continue every 6 weeks (Q6W; ± 1 week) relative to the subject's first dose regardless of any treatment delay incurred.

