5 STUDY ASSESSMENTS AND PROCEDURES

5.1 Flow Chart/Time and Events Schedule

Study assessments and procedures are presented in Table 5.1-1, Table 5.1-2, and Table 5.1-3. In limited instances, scheduled events can occur outside of the indicated timeframes, but BMS should be notified.

Procedure ^a	Screening Visit D-28 to D-1	C1D1	C1D2	C1D4 ^b	C1D8	C1D15	Notes		
Eligibility Assessments									
Informed Consent	Х						A subject is considered enrolled only when a protocol-specific informed consent is signed. In BMS-986183 dose expansion (Part 2) and BMS-986183 and nivolumab dose expansion (Part 4), if allowed by institutional practices, sites are encouraged to use a prescreening consent for the GPC-3-expressing tumor analysis. Other screening procedures should not be performed before the GPC-3-expressing tumor analysis is available for the determination of subject eligibility. Refer to Section 3.1 for additional details on screening.		
IRT Assignment	Х								
Inclusion/Exclusion Criteria	Х						Assessed during screening period. All inclusion/exclusion criteria must be met for subjects to participate in the study.		
ECOG	Х	X					Refer to Appendix 5 and Section 3.3.1. For Screening, must be within 14 days prior to treatment assignment.		
Medical History	Х						Include any toxicities or allergy related to previous treatments, smoking history, asthma, chronic obstructive pulmonary disease, history of hepatic encephalopathy. Includes detailed medical history of potential risk factors for potential events such as pulmonary-related events, cardiovascular history, neurological toxicity, infusion or hypersensitivity reactions, and smoking history. Ensure documentation of hepatitis risk factors.		
History of Alcohol use	Х								
Child-Pugh Score	Х	Χ					See Appendix 4 for scale		
Prior Treatments	X						Including prior cancer treatment regimens		
Safety Assessments									
Full PE	X	X					For Screening, must be within 14 days prior to treatment assignment. If the screening full PE is performed within 24 hours prior to dosing on Day 1, then a single exam may count as both the screening and predose evaluation.		

Table 5.1-1:Screening and Cycle 1 Procedural Outline (CA015003)

Procedure ^a	Screening Visit D-28 to D-1	C1D1	C1D2	C1D4 ^b	C1D8	C1D15	Notes

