Vital Signs ^e	X	X	X	X		Body temperature, blood pressure, and heart rate (if Day 0 and C1D1 coincide, record vital signs once).
ECGs	Х	X	X	Х		ECGs should be recorded after the subject has been supine for at least 5 minutes.
ECHO or MUGA	X		X			Must include a quantitative assessment of left ventricular ejection fraction and utilize the same modality for any subsequent assessments. ECHO/MUGA may be assessed up to 72 hours prior to the first dose. Also perform as clinically indicated.
Laboratory Tests	X	X	X	X		Day 0 laboratory values should be obtained within 14 days prior to the start of study drug. If the Day 0 laboratory tests are performed within 72 hours prior to dosing on Day 1 then a single exam may count as both the Day 0 and predose evaluation. Repeat the following if > 6 months since last treatment: hepatitis B surface antigen and hepatitis C antibody (if hepatitis C antibody is positive reflex to hepatitis C RNA) or hepatitis C RNA will be done at screening. Note: Testing for HIV-1 and HIV-2 must be performed at sites where mandated by local requirements.

Procedure ^a	Day 0 b,c	C1 and Beyond D1	ΕΟΤ	FU (30, 60, and 100 Days after Last Dose) (30- and 60-day FU: ± 5 days) (100-day FU: ± 10 days)	Survival FU ^d (±2 weeks)	Notes		
						Urine - Day 1 only, unless clinically indicated. See Section 5.3.2.		
Viral Biomarkers(for HBV and HCV)	Х	Х	Х	Х		For HCV infected, HCV RNA on treatment For HBV infected, HBV DNA on treatment		
Coagulation Panel	Х	Х	Х	Х				
Troponin T or I	Х					As clinically indicated		
Thyroid Panel including TSH, free T3, and free T4	Х	X See note				To be done Q6W. See Section 5.3.2.		
Pregnancy Test	Х	Х	Х	Х		For WOCBP only; see Section 5.3.2.		
PK and Immunogenicity Assessments See Section 5.5.								
Biomarker Assessments See Section 5.6.								
Tumor Assessment Tumor Imaging (See Section 5.3.1)	X		Х	X ^f	X ^g	Day 0 must be within approximately 30 days of C1D1. Then at the start of Cycle 3 and then Q6W thereafter (± 1 week). Scans must be de-identified. See Section 5.3.1.		
Concomitant Treatments	Х	Х	Х	X ^h		Medications administered within 4 weeks of dosing and all antiviral medications taken for any length of treatment 100 days after the last dose of study drug.		

Procedure ^a	Day 0 b,c	C1 and Beyond D1	ЕОТ	FU (30, 60, and 100 Days after Last Dose) (30- and 60-day FU: ± 5 days) (100-day FU: ± 10 days)	Survival FU ^d (±2 weeks)	Notes		
Adverse Event Reporting				(100 uuy 1 0. 2 10 uuys)				

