5.4.1 Primary Efficacy Assessment

Tumor measurements with CT and/or MRI, as appropriate, will be conducted at screening and Q6W (± 1 week) during the treatment period. Tumor measurements should be conducted earlier, if clinically indicated. Subjects with SD, PR, or CR at EOT undergo tumor assessment via CT/MRI scans every 3 to 4 months during survival follow-up until progression, death, or initiation of new treatment (whichever occurs first). Tumor measurements will be collected in all subjects until progression or the subject's discontinuation from the study as per Table 5.1-1 and Table 5.1-2. Tumor response and progression will be evaluated in this study using RECIST v1.1 (Appendix 6).⁸¹ Initial response assessment of PR or CR must be confirmed by a consecutive assessment no less than 4 weeks (28 days) later.

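### The stable-disease minimum (7 or about 8 weeks from an undefined study entry) does not fit the 6-weekly scans, so the SD versus PD/not-evaluable split in best overall response depends on scan timing and an unstated choice

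*Protocol*

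**What the plan says.** Protocol Appendix 6 Section 4.3 sets the condition for SD when responses need confirmation: "measurements must have met the SD criteria at least once after study entry at a minimum interval of 7 weeks or approximately 8 weeks". It does not say which of the two values applies, or what date counts as study entry.

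The scan schedule is in other sections. Protocol Section 5.4.1 says tumor measurements "will be conducted at screening and Q6W (± 1 week) during the treatment period". Section 4.5.4 fixes the anchor: "The end of cycle tumor assessments will continue every 6 weeks (Q6W; ± 1 week) relative to the subject's first dose". Table 5.1-3 (retreatment and extension) puts the first on-treatment scan at the start of Cycle 3, which is 2 × 21 = 42 days after first dose.

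The text points to two possible start dates. Appendix 6 Section 5.1 measures the duration of SD from the start of treatment. The notes to Table 5.1-1 in Section 5.1, however, place enrollment at consent: "A subject is considered enrolled only when a protocol-specific informed consent is signed". Section 3.1 adds "The screening period will last for up to 28 days", so consent can come up to four weeks before first dose.

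BOR is a secondary endpoint (Protocol Section 8.3.2) and is tabulated by dose and regimen (Section 8.4.2). SAP Section 4.2.1 defines BOR without a minimum SD interval or a start date for one.

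**The concern.** A programmer deriving BOR has to choose between 7 and 8 weeks and between first dose and consent. The visible plan makes neither choice. Counted from first dose, both minimums lie beyond the nominal first scan. A subject who is stable at that scan and has progressed at the next one then fails the SD rule and would be expected to appear as PD or not evaluable.

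What is at stake is how subjects divide between SD and PD/not evaluable in the BOR table. Two subjects with the same tumor course could be classified differently because one was scanned a few days later or, under a consent anchor, had a longer screening period.

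**Working it through.** **Inputs**
- SD minimum: 7 weeks = 49 days, or about 8 weeks, taken here as 56 days (Appendix 6 Section 4.3). Reading the approximate value as exactly 56 days is an assumption.
- First scan: 6 weeks ± 1 week from first dose (Sections 4.5.4 and 5.4.1), so 42 ± 7 = days 35 to 49, which is 15 possible days.
- Gap from study entry to first dose: 0 days if entry means first dose. If it means consent, the gap can be up to 28 days (Section 3.1); 1, 7, 14 and 28 days are illustrative.

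**Step 1: which first scans can qualify.** A scan on day *d* after first dose, with study entry *e* days before first dose, meets a minimum of *m* days if *d* + *e* ≥ *m*.

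| Study entry | Window days meeting 49 | Window days meeting 56 | Nominal day 42 |
|---|---|---|---|
| First dose (*e* = 0) | 1 of 15 (day 49) | 0 of 15 | fails both (7 and 14 days short) |
| 1 day before | 2 of 15 | 0 of 15 | fails both |
| 7 days before | 8 of 15 | 1 of 15 | meets 49, fails 56 |
| 14 days before | 15 of 15 | 8 of 15 | meets both |
| 28 days before | 15 of 15 | 15 of 15 | meets both |

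**Step 2: the second scan.** 84 ± 7 = days 77 to 91. Every day in that window meets both minimums under every anchor. The rule therefore matters for subjects whose only scan meeting SD criteria is the first.

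**Step 3: how many subjects could be involved.** The documents give no PFS assumption. Assume exponential PFS with median *M* weeks and hazard λ = ln 2 / *M*. The proportion with an event between weeks 6 and 12 is exp(−6λ) − exp(−12λ):

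| Assumed median PFS | exp(−6λ) − exp(−12λ) | Out of 50 subjects |
|---|---|---|
| 8 weeks | 0.595 − 0.354 = 0.241 | about 12 |
| 12 weeks | 0.707 − 0.500 = 0.207 | about 10 |
| 16 weeks | 0.771 − 0.595 = 0.177 | about 9 |
| 24 weeks | 0.841 − 0.707 = 0.134 | about 7 |

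These are upper bounds on the sequence SD at week 6 then PD at week 12. They also count deaths in the interval and subjects who were in response at week 6. They apply only if the interval runs from first dose and the first scan is too early to qualify.

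**Step 4: what does not move.** Objective response rate counts only complete and partial responses (Section 8.3.2). PFS uses documented progression or death. The expansion-cohort adaptations use responses (Section 8.1.2). None of these depends on the SD category.

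**The case against.** A reader might infer that stable disease at the first scheduled scan followed by progression can never be reported as SD. The documents do not support that. A day-49 scan is inside the allowed window and meets the 7-week value. If study entry means consent two weeks before dosing, every in-window scan meets 7 weeks; at four weeks before, every one meets both values. The word never holds only if the minimum is 8 weeks and the count starts at first dose.

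Three further points are fair:
- Section 4.3 refers to Table 4.3-1 for how sequences of assessments become a BOR, and the body of that table is not in the public text. How SD followed by PD is finally labeled cannot be confirmed. The public SAP text also shows no body for its efficacy analyses. Neither gap is counted against the plan.
- Requiring SD to last beyond the first scan is a legitimate definition. The documents give no rationale, so nothing can be said about whether the interval was deliberate.
- The impact is narrow. Disease control rate appears only in the protocol's abbreviation list; no analysis of it is visible. There is no formal hypothesis testing.

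These points limit the size of the problem but do not remove it. The two values and the undefined start remain. The open anchor makes the classification less reproducible. A rule meant to require SD through the second scan would sit at days 77 to 91. As written, the 7-week value separates a first scan on day 48 from one on day 49 when counted from first dose.

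**Conclusion.** The point stands as a misfit between a stated rule and the trial's own schedule. The SD minimum has two values and no defined start. Counted from first dose, which is the anchor for scans and PFS and the date from which BOR is recorded, an on-time week-6 scan misses both values. Only 1 of 15 window days meets 7 weeks and none meets 8.

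Its reach is limited to the SD versus PD/not-evaluable split in a descriptive tabulation of a secondary endpoint. The share of subjects involved is at most about 13% to 24%, assuming exponential PFS with a median between 24 and 8 weeks, a first-dose anchor and first scans made on time. It is worth correcting because the category cannot be reproduced from the visible text.

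**What to change.** In Protocol Appendix 6 Section 4.3 and SAP Section 4.2.1, state one minimum interval and its start date. A value that fits the schedule is at least 35 days from first dose, the first scheduled scan less its window (42 − 7). Some minimum is still needed because Section 5.4.1 allows unscheduled early scans: "Tumor measurements should be conducted earlier, if clinically indicated". Thirty-five days excludes scans made before the window opens and admits every in-window first scan.

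The cost is one sentence in each document. The downside is that SD becomes more inclusive. To offset this, show beside it the number of subjects whose SD lasts through the second scan, at about 12 weeks.
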